12.1.2 Definitions for Statistical Data Analysis

Baseline:

In general, baseline will be the last available time-point prior to Day 1, 06:30 AM.

THS 2.2 Menthol users:

Subjects switching from mCC to THS 2.2 Menthol whose product use pattern categorization is primarily THS 2.2 Menthol or predominantly THS 2.2 Menthol over a defined period will be considered as THS 2.2 Menthol users during that period. See Section 12.3 for further details on the product use.

Dual use:

Subjects switching from mCC to THS 2.2 Menthol whose product use pattern categorization is dual mostly THS 2.2 Menthol, dual balanced or dual mostly CC over a defined period will be considered as dual users. See Section 12.3 for further details on the product use.

CC users:

Subjects switching from mCC to THS 2.2 Menthol or subjects continuing to use mCC whose product use pattern categorization is primarily CC or predominantly CC over a defined period will be considered as CC users during that period. See Section 12.3 for further details on the product use.

Smoking abstinence:

Data and information contained in this document are considered to constitute trade secrets and confidential commercial information, and the legal protections provided to such trade secrets and confidential information are hereby claimed under the provisions of United States law. No part of this document may be publicly disclosed without the written consent of Philip Morris International.

Smoking abstinence during a defined period is defined as using no tobacco-containing product as reported by the subject on the electronic diary.

Non-compliance to randomization arm:

- **Confinement:**
Use of any nicotine or tobacco-containing product other than the assigned product.
Exhaled CO breath test >10 ppm for subjects from the SA arm
- **Ambulatory:**
Non-compliance in the THS 2.2 Menthol and SA arms will be defined in reference to the time period
 -]Day 6-Day 30 Visit]
 -]Day 30 Visit-Day 60 Visit]
 -]Day 60 Visit-Day 90 Visit]as the use of more than 2 CC during a single day within a time period or the use of on average more than 0.5 CC per day over the exposure study.

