### 6.3.3 Compliance to Product Allocation

During the confinement period, compliance to product/regimen allocation (exclusive use of THS 2.2 Menthol and mCC in THS 2.2 Menthol and mCC arms, respectively, and full abstinence from smoking in the SA arm) will be ensured by strict distribution of each

Philip Morris Products S.A.

Protocol ZRHM-REXA-08-US

Statistical Analysis Plan

Final v 3.0 / 29 May 2015

Confidential

Page 30 of 122

Tobacco Stick/mCC when requested by the subject. During the ambulatory period, the subjects randomized to the THS 2.2 Menthol arm will be instructed to exclusively use THS 2.2 Menthol and subjects randomized to the SA arm will be instructed to abstain from smoking.

In addition, in subjects in the SA arm, the compliance will be chemically verified in confinement using exhaled CO breath test. The cut-off point for the CO breath test value to distinguish mCC use versus SA use will be 10 ppm (Benowitz et al. 2002). No subjects from the SA arm will be withdrawn from the study if their exhaled CO breath test results are >10 ppm.

[figure not shown]

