### 6.3.3.2 Abstinence from mCC use

In order to further optimize the assessment of BoExp and increase the comparability of the levels of BoExp between THS 2.2 Menthol and SA the confounding effects of the use of any other tobacco or nicotine containing product (other than the assigned product) needs to be controlled for. Therefore a subject will be considered abstinent based on the following categorization:

- “Abstinence”: full abstinence from tobacco or nicotine containing product use other than the assigned product, biochemically verified with CO breath test ::10ppm.
- “Predominantly abstinence”: not more than 0.5 uses of any tobacco or nicotine containing product (other than the assigned product) per day on average and no more than two uses on a single day.
- “No abstinence”: more than 0.5 uses of any tobacco or nicotine containing product (other than the assigned product) per day on average or more than two uses on a single day.

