**Table 25: Stratification Labels**

Stratification Factor	Definition
Product preference (which product the subject would prefer to be randomized to).	THSm2.2 (THS 2.2 Menthol) mCC SA NP (No preference)
Sex	Male Female
Daily mCC consumption (per day)	10-19 >19
Safety Time Periods	Pre-Randomization period ([Product trial – Randomization]) Randomized period Confinement ([Day 1-Day 6 confinement] ) Ambulatory ([Day 6 ambulatory-Day 90 Visit]) Safety Follow-up ([Day 90 Visit – End of Study])
Product Use Time Periods	Period 1 ( [Day 1-Day 6 confinement] ) Period 2 ( [Day 6 ambulatory-Day 30 Visit] ) Period 3 ( ]Day 30 Visit-Day 60 Visit] ) Period 4 ( ]Day 60 Visit-Day 90 Visit] )
Product Use Categories for mCC arm	CC Only (Exclusively CC) CC Dual (Use of other products)
Product Use Categories for SA arm	Abstinent Predominantly Abstinent Not Abstinent
General Product Use Categories for THS 2.2 Menthol arm	THS 2.2 [70-100%] Dual ]30-70%[ CC [0-30%]

PP SetDetailed Product use Categories for THS 2.2 Menthol	Primarily THS 2.2 ([95-100]%) Predominantly THS 2.2 ([70-95]%) Dual Mostly THS 2.2 ([60-70]%) Dual Balanced ([40-60]%) Dual Mostly CC ([30-40]%) Predominantly CC ([5-30]%) Primarily CC ([0-5]%)
---	---

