#### 12.6.4.2 Adverse Events

A product emergent AE is defined as an AE that occurs after first product use or that is present prior to first product use and becomes more severe after first product use. All other AEs will not be summarized but provided in listings only.

All AEs occurring from the signing of informed consent will be recorded electronically. However, only product emergent AEs will be summarized. The AE listings will include all AEs captured in the database at any time during the study (including those from subjects who were not in the safety population).

In general, AE summary tables reporting the number of events and the number and percentage of subjects reporting at least one AE will be produced by randomization arm for the Pre-Randomization and Randomized periods, as reported in Section 12.6.4.1 “Safety Reporting”. AE data during the Randomized period will also be presented stratified by Confinement, Ambulatory, and Safety Follow-up.

Ambulatory AE data will also be reported by product use category (see Table 25) defined on product use over the whole ambulatory period. In particular, the general product use categories for THS 2.2 will be used, and the [Predominantly Abstinence] and [Smoking Abstinence] categories will be presented for THS 2.2 Menthol and mCC arm if at least one subject is associated to these categories.

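### The ambulatory AE tables show abstinence categories in the THS 2.2 Menthol and mCC arms, but the SAP definition ignores use of the assigned product, so active users can be labelled abstinent or predominantly abstinent

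*SAP*

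**What the plan says.** SAP 12.6.4.2 reports ambulatory AEs by the product use categories of Table 25, with each subject's category set over the whole ambulatory period. For the two product arms it adds that "the [Predominantly Abstinence] and [Smoking Abstinence] categories will be presented for THS 2.2 Menthol and mCC arm if at least one subject" is associated with them.

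Table 25 gives each arm its own set of categories. The THS arm has THS 2.2 [70-100%], Dual and CC, based on the percentage of THS use. The mCC arm has CC Only and CC Dual. The abstinence set appears only under "Product Use Categories for SA arm".

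The SAP defines the abstinence categories in 6.3.3.2, headed "Abstinence from mCC use":

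- Full abstinence is "full abstinence from tobacco or nicotine containing product use other than the assigned product, biochemically verified with CO breath test" at or below 10 ppm. The comparison sign is garbled in the text, and this reading matches the split in Table 15.
- Predominant abstinence is "not more than 0.5 uses of any tobacco or nicotine containing product (other than the assigned product) per day on average", with at most two such uses on any one day. It carries no CO condition.

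SAP 6.3.3 states the purpose of the CO limit: "The cut-off point for the CO breath test value to distinguish mCC use versus SA use will be 10 ppm".

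Protocol 12.1.2 has a different definition with no exception for the assigned product: "Smoking abstinence during a defined period is defined as using no tobacco-containing product as reported by the subject on the electronic diary".

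**The concern.** In the SA arm, leaving the assigned product out of the count does no harm, because no product is assigned. In the THS and mCC arms it removes from the count the very product the subject is using. A rule written for one arm is carried into two others where it no longer measures abstinence.

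Protocol 12.4.3 calls for safety by actual exposure, and SAP 10 and 10.3 commit to product use categories. Tables 15.2.6.2, 15.2.6.4, 15.2.6.6, 15.2.6.8, 15.2.6.11 and 15.2.6.14 use them, and several are in the package for the medical safety officer (SAP 13.2). If the definition is programmed as written, AEs of active users would appear under an abstinence heading, or the same subject would be counted in two columns.

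**Working it through.** The plan states no figure here, so the check applies the definitions to example subjects.

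**Inputs**

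- Full abstinence (SAP 6.3.3.2): zero uses of products other than the assigned one, and CO at or below 10 ppm.
- Predominant abstinence (SAP 6.3.3.2): such uses at most 0.5 per day on average and at most 2 on any day.
- THS percentage (SAP 6.3.3.1): 100 × THS / (THS + CC).
- Protocol 12.1.2: abstinent if no tobacco-containing product is used.
- The daily uses and CO values below are assumptions, chosen only to exercise the rules.

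| Subject | Other products per day | CO (ppm) | SAP 6.3.3.2 | Table 25, own arm | Protocol 12.1.2 |
|---|---|---|---|---|---|
| THS arm, 15 sticks, no CC | 0 | 4 | Full (also meets predominant) | THS 2.2: 100 × 15/15 = 100% | Not abstinent |
| THS arm, 15 sticks, no CC | 0 | 12 | Predominant only | THS 2.2: 100% | Not abstinent |
| THS arm, 15 CC, no sticks | 15 | 20 | Not abstinent | CC: 100 × 0/15 = 0% | Not abstinent |
| THS arm, no product | 0 | 3 | Full (also meets predominant) | Undefined: 0/0 | Abstinent |
| mCC arm, 15 mCC only | 0 | 20 | Predominant only | CC Only | Not abstinent |
| mCC arm, 10 mCC only | 0 | 9 | Full (also meets predominant) | CC Only | Not abstinent |
| mCC arm, no product | 0 | 3 | Full (also meets predominant) | Neither label fits | Abstinent |

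**What this shows**

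1. Four of the seven example subjects are active users of the assigned product who fall in an abstinence category (rows 1, 2, 5 and 6). Protocol 12.1.2 calls none of them abstinent.
2. The CO condition matters. The continuing smoker at 20 ppm fails full abstinence but still meets predominant abstinence, because 0 ≤ 0.5, 0 ≤ 2, and that category has no CO test.
3. Those four subjects also hold a Table 25 category for their own arm. The SAP does not say which category prevails.
4. Subjects who use no product have no other place: the THS percentage is 0/0, and neither mCC label describes them. The abstinence columns are therefore needed for them.

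**Check of the remedy.** Counting all tobacco products including the assigned one, the daily totals in row order are 15, 15, 15, 0, 15, 10 and 0. Only rows 4 and 7 then reach an abstinence column, which agrees with Protocol 12.1.2 in all seven rows.

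**The case against.** The best defence is that the intended meaning can be inferred. The label [Smoking Abstinence] matches the term in Protocol 12.1.2 rather than the labels in SAP 6.3.3.2 or Table 25, and the SAP says it supplements the protocol. Showing the columns only if some subject belongs there suggests rare cases, that is, subjects who stopped. If every exclusive user qualified, the condition would have little purpose. Protocol 12.4 keeps exclusive THS, dual, exclusive mCC and SA groups apart. Section 6.3.3.2 was written to make BoExp levels comparable between THS and SA. Column rules may also sit in the separate table shells (SAP 3).

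Most of this stands as evidence of intent, but it does not close the gap. Protocol 12.1.2 gives no meaning to [Predominantly Abstinence], and the only SAP wording for that category admits continuing smokers. No precedence rule appears in either document. SAP 9 also records that the study team was accidentally unblinded, which favours a written rule over one settled in programming.

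Three stronger readings are tempting, and the documents do not support them:

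- **Continuing smokers in general count as fully abstinent.** They do not. Anyone above 10 ppm fails that category, and the cut-off was set to separate mCC use from abstinence.
- **A stated majority of those labelled abstinent would be active users.** A reader might combine the expected 40 compliant THS subjects of 80 with the 40 mCC subjects (SAP 8). Those are per-protocol retention assumptions. Ambulatory non-compliance is defined only for the THS and SA arms, counts CC only, and is judged per period. Section 6.3.3.2 counts any tobacco or nicotine product, and 12.6.4.2 uses the whole ambulatory period. Neither document gives an expected number of quitters.
- **Subjects who quit could not be identified.** Individual AEs (listing 15.3.6.1) and daily ambulatory product use (listing 15.3.2.1.3) are both listed.

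**Conclusion.** The point holds as a definitional defect that should be corrected. SAP 12.6.4.2 uses two categories in arms for which the SAP gives no workable definition. Applied literally, its only definition places exclusive THS users with CO at or below 10 ppm in full abstinence. It places subjects smoking only mCC in predominant abstinence, and in full abstinence if their CO is at or below 10 ppm. These subjects overlap with THS 2.2 [70-100%] or CC Only, with no rule of precedence.

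The reach is limited to the descriptive ambulatory AE tables by product use category. AE tables by randomization arm, the BoExp analyses and the primary analysis are untouched. The number of subjects affected cannot be estimated reliably from the documents.

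The conclusion assumes that the table shells, which were not available, do not already settle the matter, and that the garbled CO sign means at or below 10 ppm.

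**What to change.** In SAP 12.6.4.2 and Table 25, for the THS 2.2 Menthol and mCC arms:

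- Define both categories on use of all tobacco products, including the assigned one. *Abstinent*: no use over the ambulatory period, in line with Protocol 12.1.2. *Predominantly abstinent*: at most 0.5 uses per day on average and at most 2 on any day.
- Apply to *Abstinent* the same CO verification (at or below 10 ppm) as in the SA arm, so that the label means the same in all three arms.
- State how NRT is counted. SAP 6.3.3.2 refers to tobacco or nicotine products, Protocol 12.1.2 to tobacco only.
- Give *Abstinent* precedence over *Predominantly abstinent*, and both precedence over THS 2.2/Dual/CC and CC Only/CC Dual, so that each subject is in exactly one column.

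The cost is a short clarification in the SAP and one change to the dataset derivation. The diary records all products in all arms, and exhaled CO is measured in all arms at the Day 30, 60 and 90 Visits, so no new data are required.

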##### 12.6.4.2.1 All Adverse Events

A general summary table of AEs will be presented including:

- The number of events and the number and percentage of subjects reporting at least one AE.
- The number of events and the number and percentage of subjects reporting at least one study product –related AE, broken down by product relatedness (related to THS 2.2 Menthol/ mCC) and expectedness (expected for THS 2.2 Menthol / mCC).
- The number of events and the number and percentage of subjects reporting at least one AE broken down by severity including each subject only once with his worst severity.
- The number of events and the number and percentage of subjects reporting at least one SAE.
- The number of events and the number and percentage of subjects reporting at least one AE leading to any action taken, broken down by action taken related to the product (product use interrupted, product use reduced, product use stopped, not applicable, none), treatment given (yes, no), study discontinuation, other action taken.
- The number of events and the number and percentage of subjects reporting at least one AE related to study procedure

Additional summary tables of AEs will be presented with a breakdown of the number of events, as well as the number and percentage of subjects reporting each AE, categorized by SOC and PT coded according to the MedDRA dictionary (version 16.0).

If a subject has more than one occurrence of the same AE, the subject will be counted only once within a PT with the worst occurrence based on the presentation (e.g., for presentation by severity = most severe, for presentation by relationship = most related). Missing information on the intensity of AE will be counted as severe.

The data will be presented in the below outputs:

TFL number	Title
TABLES	
15.2.6.1	Summary of Adverse Events– Safety Population
15.2.6.2	Summary of Adverse Events by Product Use Category in Ambulatory Period – Safety Population
15.2.6.3	Summary of Adverse Events by System Organ Class and Preferred Term – Safety Population
15.2.6.3.1	Summary of Adverse Events (Incidence >5% in any Study Arm) by System Organ Class and Preferred Term – Safety Population
15.2.6.4	Summary of Adverse Events by Product Use Category, System Organ Class and Preferred Term – Safety Population
15.2.6.5	Summary of Adverse Events by System Organ Class, Preferred Term and Relationship to Study Product Exposure and Expectedness – Safety Population
15.2.6.6	Summary of Adverse Events by Product Use Category, System Organ Class, Preferred Term and Relationship to Study Product Exposure and Expectedness – Safety Population
15.2.6.7	Summary of Adverse Events Leading to Study Product Discontinuation, Interruption, or Reduction by System Organ Class and Preferred Term – Safety Population
15.2.6.8	Summary of Adverse Events Leading to Study Product Discontinuation, Interruption, or Reduction by Product Use Category, System Organ Class and Preferred Term – Safety Population
15.2.6.9	Summary of Adverse Events Related to Study Procedure by System Organ Class and Preferred Term – Safety Population
15.2.6.10	Summary of Adverse Events by System Organ Class, Preferred Term and Severity – Safety Population
15.2.6.11	Summary of Adverse Events by Product Use Category, System Organ Class, Preferred Term and Severity – Safety Population
LISTINGS	
15.3.6.1	Listing of Adverse Events

#### 12.6.4.2.2 Serious Adverse Events (Including Deaths)

A summary table of SAEs will be presented using the same approach as for AEs (see Section 12.6.4.2 “Adverse Events”), and including the number of events and the number and percentage of subjects reporting at least one SAE broken down by seriousness criteria (fatal, life-threatening, requires hospitalization, results in disability/incapacity, congenital anomaly/birth defect).

SAEs will also be listed in separate listings by product.

The data will be presented in the below outputs:

TFL number	Title
TABLES	
15.2.6.12	Summary of Serious Adverse Events by System Organ Class and Preferred Term – Safety Population
LISTINGS	
15.3.6.2	Listing of Serious Adverse Events

#### 12.6.4.2.3 Adverse Events Leading to Discontinuation

Summaries will be presented for AEs leading to discontinuation, by product as described in Section 12.6.4.2 “Adverse Events”,

AEs leading to discontinuation will also be listed in separate listings by product.

The data will be presented in the below outputs:

TFL number	Title
TABLES	
15.2.6.13	Summary of Adverse Events Leading to Study Discontinuation by System Organ Class and Preferred Term – Safety Population
15.2.6.14	Summary of Adverse Events Leading to Study Discontinuation by Product Use Category, System Organ Class and Preferred Term – Safety Population
LISTINGS	
15.3.6.3	Listing of Adverse Events Leading to Study Discontinuation

#### 12.6.4.2.4 Laboratory Abnormalities

The shift in toxicity grades from baseline to worst grade recorded while in the exposure period will be presented in tables for the clinical chemistry, hematology and urinalysis parameters. Details related to the toxicity grading of laboratory abnormalities are available in Section 12.6.4.3 “Clinical laboratory Evaluation”.

The data will be presented in the below outputs:

TFL number	Title
TABLES	
15.2.6.16	Summary of Clinical Chemistry Parameters – Safety Population
15.2.6.17	Summary of Hematology Parameters – Safety Population
15.2.6.18	Summary of Urinalysis Parameters – Safety Population

#### 12.6.4.2.5 THS2.2 Menthol Device Events

All events relating to the device type will be listed for each subject, including event description, device type the event relates to, severity of event, AE relationship, proposed solution and onset/stop dates/times. Device events will be classified according to PMI controlled terminology.

A summary table of device events will be presented by product, including:

- Number of device events and the number and percentage of subjects reporting at least one device event.
- Number of device events and the number and percentage of subjects categorized by severity of device event (minor, major)
- Number of device events and the number and percentage of subjects categorized by AE relationship (related, not related)
- Number of device events and the number and percentage of subjects categorized by event description (Cigarette Holder (CH) stops heating, CH does not charge, CH led blinking red, Smoking experience does not start, electronic malfunction, other)

Device events and inventory will be listed by product. Data collected during Screening will be listed but not summarized.

The data will be presented in the below outputs:

TFL number	Title
TABLES	
15.2.6.15	Summary of THS 2.2 Menthol Device Events – Safety Population
LISTINGS	
15.3.6.5	Listing of THS 2.2 Menthol Device Events and Malfunctions

#### 12.6.4.3 Clinical Laboratory Evaluation

**Table 27** below lists the hematology, clinical chemistry and urine analysis parameters to be assessed in this study.

**Table 27: List of Laboratory Safety Parameters**

Hematology	Clinical chemistry	Urine analysis
Hematocrit	Albumin	pH
Hemoglobin	Total protein	Bilirubin
Mean corpuscular hemoglobin	Alkaline phosphatase	Glucose
Mean corpuscular hemoglobin concentration	Alanine aminotransferase	Nitrite
Mean corpuscular volume	Aspartate aminotransferase	Red blood cell traces
Platelet count	Blood urea nitrogen	Protein
Red blood cell count	Creatinine	Specific gravity
WBC count Differential	Gamma-glutamyltransferase	
WBC count:	Fasting glucose	
• Neutrophils	Lactate dehydrogenase	
• Basophils	Potassium	
• Eosinophils	Sodium Total	
• Lymphocytes	bilirubin Direct	
• Monocytes	bilirubin	
	Total cholesterol	
	Triglycerides	

Any clinical safety laboratory test result that is outside of the normal reference range will be reviewed by the principal investigator (PI) and assessed for clinical relevance. If the PI considers the abnormal result to be of clinical relevance, then it must be recorded as a concomitant disease at Screening, or if not present at Screening, as an AE during the study. If the condition worsens from screening to after product-use it will be recorded as an AE.

The grading scheme used in the Common Terminology Criteria for Adverse Events and Common Toxicity Criteria [CTCAE] version 4.03) will be used by the PI to assess abnormal laboratory values. These CTCAE grades will be derived programmatically in the creation of the datasets.

Laboratory data will be summarized and listed at Screening and Day 0 for the Pre-Randomization period; and at Baseline, Day of Discharge (Day 6), Day 30 Visit, Day 60 Visit and Day 90 Visit for the Randomized period data together with changes from Baseline. The number and percentage of subjects with normal results, high/low results and abnormal clinical significant result (as defined by PI comment), and CTCAE toxicity grading will be tabulated for laboratory parameters, together with shift in normality (Normal, Abnormal NCS, Abnromal CS) and in CTCAE toxicity grading from Baseline.

Listings for the clinical laboratory data will include the following information: change from Baseline, normal/ high/low (with respect to the reference range), abnormal clinically significant (as defined by the PI comments) and shift from Baseline, the PI comments, the CTCAE grade and the shift in CTCAE grade. Only CTCAE grades greater than zero will be presented.

The data will be presented in the below outputs:

TFL number	Title
TABLES	
15.2.6.16	Summary of Clinical Chemistry Parameters – Safety Population
15.2.6.17	Summary of Hematology Parameters – Safety Population
15.2.6.18	Summary of Urinalysis Parameters – Safety Population
LISTINGS	
15.3.6.6	Listing of Clinical Chemistry Data, Shift, Changes from Baseline and CTCAE grades
15.3.6.7	Listing of Hematology Data Shift, Changes from Baseline and CTCAE grades
15.3.6.8	Listing of Urinalysis Data Shift, Changes from Baseline and CTCAE grades

